### **6.6.2 Primary Efficacy Endpoints**

The Primary study outcome assessments will be determined based on differences in the mean VAS ratings on a 0-10cm VAS scale for comfort (the scale ranges from 0-100, and 0 = no pain or discomfort, and 100 = extreme discomfort or worst pain imaginable). Statistical methods employed to detect differences between the experimental and the control groups, for the below outcomes, may include a t-test, Chi-Square test, and Fisher's Exact test. Test for normality and equality of variances may be used for continuous parameters. If data are found to fail one or both, then nonparametric methods may be employed, eg, Wilcoxon Rank Sum test. For assessments including crossovers, a relevant method accounting for period effect, repeated measures, and randomized order may be utilized.

Analyses outlined below will be done for the average of patient scores.

One of the following analyses will be employed as the primary analysis of the primary efficacy endpoint:

Statistical Analysis Plan		Page 11 of 18
Sponsor Neuronetics	Study Comfort Start	Version 1.0

The difference in the change in Visual Analog Scale scores for Comfort after rTMS stimulation between treatments administered with the Dash protocol and with New feature enabled. Comfort will be evaluated as a change for all observations between groups, observations from Baseline to end of escalation phase, observations between groups during the crossover phase and observations within a patient between treatments in the cross-over phase.

At minute 3:45, and at the end of the treatment session, the subject will be asked to complete a Visual Analog Scale (VAS), for Comfort/Pain.

- a. All over group (throughout the whole trial, Ramp phase & Crossover phase) – all VAS scores for X → Y or Y → X (similar to 1.d.ii above. Start with the average of the 3:45, 18:45 scores on each Day for each subject, then average each of the daily X averages and average each of the daily Y averages for each patient, comparing the average of the 40 X averages to the average of the 40 Y averages, a one-sided hypothesis test evaluating if the “with Comfort Start” group, X, has lower average scores)
- b. Between group comparison: Prior to cross over (reaching 120%MT): combination of the scores at 3:45 min and at the end of treatment, 18:45 min; (start with the average of the these two scores for each subject that reached 120% (average of all scores prior to & including 120%), then compare the average of the X averages (at most 20) to the average of the Y averages (at most 20), a one-sided hypothesis test evaluating if the “with Comfort Start” group, X, has lower average scores)
- a. Average of all the patient scores for all Crossover Phase treatments (start with the average of the 3:45 and 18:45 scores on each Crossover Day for each subject, then average each of the daily X averages and average each of the daily Y averages for each patient, comparing the average of the 40 X averages to the average of the 40 Y averages, a one-sided hypothesis test evaluating if the “with Comfort Start” group, X, has lower average scores)

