18.2 Analysis Plan

The primary outcome is the difference in comfort and pain observed between rTMS stimulation protocols using VAS comfort scores. The analysis will be performed on the sample of evaluable subjects, meaning those subjects with at least one post-treatment time point.

- Descriptive analysis of subject demographics and other baseline variables.

- Primary Outcome Assessment:

The Primary study outcome will be determined based on differences in the mean VAS ratings on a 0-10cm VAS scale for comfort between treatment arms.

- Secondary Outcome Assessment:

The Secondary objectives are to evaluate the ability to reach the prescribed treatment intensity, the time it takes to reach the prescribed treatment intensity, maximum treatment intensity reached, patient treatment preference and discontinuations due to treatment discomfort. Other treatment effects between the two treatment protocols will be explored.

- Comparison of the incidence, severity, and frequency of Adverse Events (AE) between the experimental and the control group will be made descriptively.
- Statistical methods employed to detect differences between the experimental and the control groups, for the above outcomes, may include a t-test, Chi-Square test, and Fisher's Exact test. For assessments including crossovers, a relevant method accounting for period effect, repeated measures, and randomized order will be utilized.
- Subgroup analysis will be performed based on initial comfort scores, group assignments or other variables.
- More detailed descriptions of the statistical methodology and analyses will be supplied in a separate SAP (statistical analysis plan).

ADMINISTRATIVE SECTION

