## 1 Introduction

This statistical analysis plan (SAP) describes the planned statistical methods to be used during the reporting and analysis of data and should be read in conjunction with the study protocol and case report forms (CRFs). Any revisions to the protocol or CRFs that impact the planned analyses may require updates to the SAP.

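### SAP 6.6.2 makes the protocol's required crossover method optional and names none; its whole-trial candidate primary analysis counts ramp days for the first-assigned treatment only

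*SAP*

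**What the plan says.** Protocol 18.2 states that for crossover assessments "a relevant method accounting for period effect, repeated measures, and randomized order will be utilized" and leaves the detail to a separate SAP. SAP 6.6.2 repeats the sentence with a weaker verb: "For assessments including crossovers, a relevant method accounting for period effect, repeated measures, and randomized order may be utilized". The tests the SAP names are a t-test of unstated type, Chi-Square and Fisher's Exact. If assumptions fail, "nonparametric methods may be employed, eg, Wilcoxon Rank Sum test".

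The SAP does not choose a primary analysis: "One of the following analyses will be employed as the primary analysis of the primary efficacy endpoint". Three candidates follow:

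- a whole-trial comparison pooling ramp and crossover days;
- a between-group comparison of scores up to 120% MT;
- a crossover-phase comparison.

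The first and third begin from daily means, "then average each of the daily X averages and average each of the daily Y averages for each patient", and then compare 40 X averages with 40 Y averages. The same section also lists "observations within a patient between treatments in the cross-over phase" among the ways comfort will be evaluated, and SAP 1 says the SAP is to be read alongside the protocol.

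On the design, Protocol 13.1 gives a ramp of 1 to 5 visits. All are on the randomized treatment, because the first switch occurs at Crossover Visit 1. Four alternating crossover sessions follow.

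**The concern.** There are two separate problems.

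First, the protocol sets an obligation and defers the method to the SAP. The SAP drops the obligation and supplies no method: no model, no period or sequence term, no paired test. The 40 X and 40 Y averages come from the same patients, yet the only nonparametric example given is for independent samples. An analyst following the SAP could run an unpaired test, which would be conservative and lose power.

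Second, the whole-trial average is unbalanced by construction. Ramp sessions enter only the first-assigned treatment's mean. With equal sequence sizes the imbalance cancels if ramp length has the same distribution in both arms. The synopsis, however, hypothesizes that SoftStart may shorten the time to prescribed intensity, and time to that intensity is a secondary objective. So the candidate is vulnerable to an effect the trial is looking for.

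The direction is unknown. Ramp starts at 90% MT, and Protocol 9.1 says intensity affects discomfort, so ramp scores could be lower, which would bias against SoftStart. Ramp also includes first exposure, so scores could be higher, which would bias toward SoftStart.

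**Working it through.** **Inputs from the documents.** N = 40, 20 per sequence, with no power, effect size or SD stated (SAP 5). Ramp length L = 1 to 5 days. The crossover phase has 4 sessions, 2 per treatment. (Protocol 10.1 has alternation continuing for 3 further treatments and SAP 4 for 4. Both schedules of events show four crossover sessions, the count used here; the two texts should be reconciled.) Candidate tests are one-sided with no level given; SAP 6.1.4 sets two-sided 0.05 as default.

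**Assumptions, none in the documents.** SD of a patient's treatment average 20 mm on the 0–100 scale; within-patient correlation rho 0.3, 0.5 or 0.8; one-sided 0.05; ramp scores 5 to 15 mm above or below crossover scores.

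**Part 1: pairing.** Paired SE = 20·sqrt(2(1−rho)/40) = 3.74, 3.16 and 2.00 mm, with power from the noncentral t on 39 df. The unpaired test works with SE = 20·sqrt(2/40) = 4.47 mm whatever rho is; its power comes from 40,000 simulated trials, 78 df.

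| True difference | rho | Paired | Unpaired |
|---|---|---|---|
| 6 mm | 0.3 | 47% | 35% |
| 6 mm | 0.5 | 59% | 33% |
| 6 mm | 0.8 | 90% | 25% |
| 10 mm | 0.3 | 84% | 76% |
| 10 mm | 0.5 | 93% | 79% |
| 10 mm | 0.8 | >99% | 89% |

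Under the null the unpaired test rejects 2.5%, 1.1% and <0.1% at a nominal 5%. The error is loss of power, not false positives.

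**Part 2: ramp weight.** The first-assigned mean rests on L + 2 days and the other on 2. The ramp share is w = L/(L+2): 1/3 = 33%, 2/4 = 50%, 3/5 = 60%, 4/6 = 67%, 5/7 = 71% for L = 1 to 5. For the other treatment it is 0%. These shares need no assumption.

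Let g be the mean ramp score minus the mean crossover score, with no true treatment difference. At 20:20 the spurious Y minus X is (w_Y − w_X)/2 × g. At g = 15 mm:

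- X-first 1 day, Y-first 2 days: (0.500 − 0.333)/2 × 15 = 1.25 mm
- 2 vs 3 days: (0.600 − 0.500)/2 × 15 = 0.75 mm
- 1 vs 3 days: (0.600 − 0.333)/2 × 15 = 2.0 mm
- equal ramps: 0

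Percentage of null trials in which a paired t-test declares X better (40,000 simulated trials per cell; ranges run over rho):

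| Ramp days, X-first vs Y-first | Ramp 5 / 10 / 15 mm higher | Ramp 5 / 10 / 15 mm lower |
|---|---|---|
| 1 vs 2 | 6–7 / 8–9 / 8–11 | 3–4 / 2–3 / 1–2 |
| 2 vs 3 | about 6 throughout | about 4 / 2–3 / 1–3 |
| 1 vs 3 | 7–9 / 9–13 / 12–18 | 2–3 / 1–2 / 0–1 |

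Equal ramps give 5% or less. A hand check of the largest cell (1 vs 3, +15 mm, rho 0.8): Y−X is shifted by −15/3 = −5 in X-first patients and +15·3/5 = +9 in Y-first patients, so the mean is +2 and the half-gap 7. The true SE is sqrt(160/40) = 2.0. The SE the test computes is about sqrt((160 + 49·40/39)/40) = 2.29. It rejects above 1.685 × 2.29 = 3.86, and P(Z > (3.86 − 2)/2) = P(Z > 0.93) ≈ 18%.

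**Sensitivity.** Simulating sessions (subject variance 400·rho, session variance 800·(1−rho)) puts that cell at 13–21% across rho. With different assumed SDs (15 mm between subjects, 10 mm per day) and g = +10 mm, the rates are 8% (2 vs 4 days), 18% (1 vs 3) and 28% (1 vs 5). At g = −10 mm they are 0.1–0.5%.

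**Does the remedy work?** With session-level data and random-intercept models, a crossover-only model rejects 4.0–5.8% of null trials, and a whole-trial model with a ramp/crossover term 4.1–5.7%, the latter assuming a constant ramp shift. A whole-trial model without that term rejects 19–35% at 1 vs 3 days and +15 mm, so a mixed model alone does not remove the bias.

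**The case against.** The SAP is to be read with the protocol, whose sentence already describes a paired or mixed analysis. The protocol names no model either. The named tests are examples, and independent-sample tests are right for the between-group ramp comparison. The power losses therefore describe a test nobody has said will be run, in a study not sized on power. All of that is fair, and it is why the charge is that an unpaired test is permitted, not planned. It does not resolve the conflict between the two verbs or supply the detail the protocol deferred to the SAP.

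On the second part, if SoftStart changes nothing, randomization gives both arms the same ramp-length distribution and the whole-trial average is unbiased. A simulation with random ramp lengths of 1 to 5 days gave 4.7% and 3.9% rejection at shifts of 10 and 15 mm (SD 20, rho 0.5). Excess rejection requires SoftStart to change ramp time while leaving comfort scores alone, and the simulations above give every patient in an arm the same ramp length. This stands as a limit on the claim. The condition is nonetheless plausible where intensity is raised to tolerance, and a faster ramp is part of the study's own hypothesis.

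The figures also depend on the assumed SDs, the level and the sign of the shift. At one-sided 0.025, 1 vs 3 days at +15 mm gives about 7–10%. A comparison over all observations is a listed endpoint evaluation, so demoting it is partly a choice of estimand. A crossover-only analysis omits patients who leave during the ramp, but they have no score on the other treatment, so a paired whole-trial comparison loses them too. Some patients enter crossover below 120% MT and continue escalating, so intensity still varies there.

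**Conclusion.** The concern holds on both parts. The conflict in wording, the missing within-patient method and the 33–71% versus 0% ramp shares come directly from the documents.

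The consequences are conditional. Power is lost only if an unpaired test is used. Bias arises only if the whole-trial candidate is chosen, ramp length differs by arm, and ramp and crossover scores differ; the documents establish none of these. Under the main assumptions (SD 20 mm, one-sided 0.05, ramp contrasts up to 1 vs 3 days, shifts up to 15 mm), the bias is at most 2.0 mm and null rejection runs from near 0% to about 18%, according to the sign of the shift. Other variance assumptions and larger ramp contrasts give higher rates.

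Because the study is exploratory, this should be fixed but does not threaten a confirmatory claim. Confidence is high on the text and the weights, lower on any particular error rate.

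**What to change.** In SAP 6.6.2:

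1. Restore the protocol's obligation by changing *may* to *will* in the crossover sentence.
2. Make the crossover-phase analysis already listed the within-patient primary candidate. Specify a linear mixed model on session-level VAS over the four crossover sessions, with treatment, session (period) and sequence as fixed effects and a random subject effect. Name the Wilcoxon signed-rank test on within-patient differences as the fallback. Reserve the independent-sample t-test and rank sum for the between-group ramp comparison.
3. Drop the simple whole-trial average as a candidate primary analysis. If whole-trial data are reported, label them supportive and fit session-level data with a phase (ramp or crossover) term.

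The cost is SAP wording only. No new data are needed, and if the default package cannot fit the model, SAP 6.1 already allows SAS 9.4 or later.

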### **6.6.2.1 Primary Analysis**

The majority of the primary efficacy endpoints will be assessed with the following hypothesis:

$H_0$ : Comfort Start Dash is equal to or inferior to Dash

$H_a$ : Comfort Start Dash is superior to Dash

Statistical Analysis Plan		Page 12 of 18
Sponsor Neuronetics	Study Comfort Start	Version 1.0

Note that some of the hypothesis testing will be two-sided, but the majority of inferential statistical testing will be looking at a one-sided alternative hypothesis that the treatment protocol with Comfort Start employed is superior to the Dash protocol without Comfort Start employed.

The endpoints will be evaluated using the mITT population.

The primary endpoints will be assessed via descriptive (unless otherwise specified) and superiority statistics.

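### SAP 6.6.2 leaves the primary efficacy analysis open among three one-sided tests, states no one-sided alpha, and does not require the choice to precede the results

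*SAP*

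**What the plan says.** **Choice.** SAP 6.6.2 introduces its list with "One of the following analyses will be employed as the primary analysis of the primary efficacy endpoint". The three entries are:
- Whole trial: each subject's X and Y averages over ramp and crossover sessions, "comparing the average of the 40 X averages to the average of the 40 Y averages".
- Ramp phase: a comparison between randomized groups, at most 20 against 20. The instruction is "start with the average of the these two scores for each subject that reached 120" (per cent of MT).
- Crossover phase only: X and Y averages per subject, compared as in the first entry.

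SAP 6.6.2.1 then uses the plural: "The majority of the primary efficacy endpoints will be assessed with the following hypothesis". Protocol 16 lists several comparisons, and Protocol 18.2 names no single one and defers detail to the SAP.

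**Alpha.** All three entries are one-sided. SAP 6.1.4 sets a two-sided 0.05 default and nothing else. SAP 6.6.2.1 adds "Note that some of the hypothesis testing will be two-sided", while "the majority of inferential statistical testing will be looking at a one-sided alternative hypothesis". It does not assign sidedness test by test.

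**Test.** SAP 6.6.2 offers a t-test, and if assumptions fail, "nonparametric methods may be employed, eg, Wilcoxon Rank Sum test". For crossover assessments, a method handling period, repeated measures and order *may* be used; Protocol 18.2 says it *will* be used. The lead-in to the list mentions both within-patient comparisons across treatments and between-group comparisons in the crossover phase.

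**The concern.** A p-value keeps its nominal error rate only if the test was fixed independently of the data. Here three different tests each qualify as the primary analysis under the plan. Choosing any of them is not a departure from the SAP, so the change procedure in SAP 7 need not be triggered. That procedure in any case asks for approval before analysis only where possible. SAP 4.2 blinds only patients, and nothing requires whoever chooses to be unaware of the results.

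The missing one-sided level is a second open choice. A reader could take one-sided 0.05, or one-sided 0.025 as the counterpart of the two-sided default. The mixed wording on pairing is a third. It affects both the error rate and, more strongly, the power of a design whose strength lies in comparing each subject with himself or herself.

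At stake is whether a superiority statement for SoftStart comfort carries the error rate it appears to carry.

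**Working it through.** The documents state no power, SD or familywise error figure, so there is none to reproduce.

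**1. Bracket by arithmetic.** With no session trend, independent session errors and the same X−Y difference in every subject, the paired crossover test and the ramp test are uncorrelated: the subject's own level cancels from the first, and the two use different sessions. The whole-trial test is strongly correlated with the crossover test (0.80–0.91 in simulation) and weakly with the ramp test (0.08–0.32). The chance that at least one of three is significant should therefore lie between that for two and that for three independent tests:
- One-sided 0.05: 1 − 0.95² = 9.75% and 1 − 0.95³ = 14.3%.
- One-sided 0.025: 1 − 0.975² = 4.9% and 1 − 0.975³ = 7.3%.

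**2. Null simulation.** From the documents: 20 subjects per sequence, 1–5 ramp sessions, four alternating crossover sessions, three one-sided tests. Assumed: between-subject SD 6–20 mm, session SD 5–15 mm, 70–100% reaching 120% MT, and trends of 0, −4, −2 or +3 mm per session. The best of three is taken after the results are seen.

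| Tests used | at 0.05 | at 0.025 |
|---|---|---|
| Paired t, no trend | 11.1–12.6% | 5.7–6.6% |
| Period-adjusted, no trend | 10.6–12.4% | 5.6–6.6% |
| Period-adjusted, with trend | 10.3–13.7% | 5.5–7.1% |
| Paired t ignoring a trend | 6.5–11.6% | 2.9–6.1% |
| Unpaired t, no trend | 4.8–8.7% | 2.3–4.2% |
| Unpaired t, with trend | 4.6–9.0% | 2.2–4.6% |
| Paired, one test picked blind | at most 5.3% | at most 2.7% |

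A separate simulation with independent errors gave 10.9–12.2% for paired tests at 0.05 with no trend. Serial correlation of 0.8 between sessions raised this to at most 13.9%.

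**3. Why pairing matters.** Take the crossover analysis with session SD 10 mm and an assumed 5 mm benefit. A subject's mean of two X sessions minus mean of two Y sessions has variance 10²/2 + 10²/2 = 100.
- Paired: SE = 10/√40 = 1.58 and 5/1.58 = 3.16. Against the critical t of 2.02 (38 df, one-sided 0.025), power is 87%.
- Unpaired, between-subject SD 10: each average has variance 100 + 50 = 150, so the test uses SE = √(2 × 150/40) = 2.74, although the true value is 1.58. Simulated power is 41%.
- Unpaired, between-subject SD 15: SE = √(2 × 275/40) = 3.71. Simulated power is 9%.

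**4. Effect of the alpha reading on power** (same analysis, critical t 1.69 or 2.02).
- Constant X−Y difference: 93% at one-sided 0.05, 87% at 0.025.
- X−Y difference varying between subjects with SD 10 mm: variance 100 + 100 = 200, SE = 14.14/√40 = 2.24, 5/2.24 = 2.24. Power is 71% and 59%.

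**The case against.** **The study is exploratory.** Protocol 18.1 and SAP 5 say the sample size serves exploratory and planning purposes, and SAP 6.6.2.1 says "The primary endpoints will be assessed via descriptive (unless otherwise specified) and superiority statistics". This lowers the stakes. It does not remove them, because the same section sets null and alternative hypotheses for superiority.

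**Nobody has said the choice will follow the results.** This is correct. A reader might infer that the sponsor plans to pick the most favourable test, and the documents do not support that. No interim analyses are planned (SAP 6.9), SAP 7 sends changes identified before analysis to an amended SAP, and SAP 4.2 concerns treatment blinding rather than the analyst's access to data. What stands is that nothing requires a prior choice.

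**The inflation is conditional.** A reader might quote 11–13% instead of 5% without qualification. That needs one-sided 0.05, which the SAP never states, together with paired tests and no neglected session trend. A trend is plausible, since intensity is escalated from 90% towards 120% MT. All SDs and trends are assumptions.

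**Pairing is not absent.** A reader might infer that the SAP is silent on pairing or plans unpaired tests. The lead-in names within-patient comparisons, the averages are formed per patient, and SAP 1 ties the SAP to the protocol, whose section 18.2 promises a repeated-measures method. The low unpaired power figures therefore describe a reading that the documents disfavour. The defect is mixed wording: between-group crossover comparisons, an unpaired rank test as fallback, and *may* against *will*.

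**The three analyses would differ anyway.** With a 5 mm benefit they disagree in 61–83% of simulated trials using period-adjusted tests, largely because their power differs. That shows that the choice matters, not that it will be misused.

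**Conclusion.** The concern holds. The primary efficacy analysis, its one-sided alpha and the timing of the choice are all unspecified, and no other section supplies them.

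If the choice follows the results and the tests are paired or period-adjusted, the false-positive rate is about 10–14% at a nominal one-sided 0.05, or about 5.5–7% at 0.025: roughly two to three times nominal. At 0.05 it is about 6.5–12% if paired tests ignore a session trend, and about 5–9% if tests are unpaired. A blind choice adds no inflation. These figures rest on the assumed SDs, trends and ramp patterns given above.

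The pairing issue is a wording conflict to reconcile. Because the SAP sets a superiority hypothesis, the choice should be settled before any outcome data are seen.

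**What to change.** Before outcome data are seen, amend SAP 6.6.2 as follows.
- Name and date one primary analysis with its alpha, for example one-sided 0.025 to match the two-sided 0.05 default. Label the other two supportive. The sponsor may name any of the three.
- Example: per subject, mean X minus mean Y VAS over the four crossover sessions, using the average of the 3:45 and 18:45 scores per session. Test it with a period-adjusted two-sequence t-test on the subject differences: average the two sequence means and use the pooled within-sequence variance (38 df with 40 subjects).
- A mixed model with treatment, session and sequence, plus random subject and subject-by-treatment effects, is a closely similar but not identical alternative that handles missing sessions. A random intercept alone is not enough: at nominal 0.025 it rejected 5.5% of null trials when the X−Y difference varied with SD 10 mm (session SD 10 mm).
- State that within-subject comparisons are paired, and change *may* to *will* for the crossover method, as in Protocol 18.2.
- Reconcile the named analysis with the mITT set in SAP 6.2. The ramp analysis drops subjects who did not reach 120% MT; the crossover analysis drops those who leave during the ramp. Report numbers and reasons by arm.

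The cost is SAP wording only, with no new data. Relative to a one-sided 0.05 reading, 0.025 raises the critical t by about 20% (1.69 to 2.02). In the example, power falls from 93% to 87%, or from 71% to 59% if the X−Y difference varies with SD 10 mm.

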13.2 Discontinuation and Withdrawal of Subjects

Subjects may withdraw voluntarily from the study at any time. They may be withdrawn from the study by the Investigator if:

- A serious adverse event (SAE) occurs.
- The Investigator believes that for safety reasons it is in the best interest of the subject to be withdrawn.
- The subject withdraws consent.
- A positive urine drug screen at any visit.
- A positive pregnancy test at any visit; the subject reports pregnancy.
- Inability to locate and quantify a motor threshold as defined in the protocol or a motor threshold above 1.6 SMT.
- Investigator sets a treatment goal below 120% of MT.

Discontinuation information [e.g., date and the reason(s) for discontinuation] must be recorded in the subject's CRF (i.e., Study Termination Record page).

Follow-up information will be obtained for subjects who experience an SAE.

Subjects withdrawn from the study will not be replaced.

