## **4.1 Randomization**

Subjects will be randomized prior to study start, to the initial treatment received prior to first crossover. Randomization will be performed using random permuted blocks of sizes 2 and 4, stratified by gender, with a 1:1 allocation ratio (Dash protocol / Dash protocol with SoftStart). A single site handling 40 total subjects is planned. Extra subjects and sites will be randomized, in the event unforeseen changes become necessary. Randomized treatment will be assigned by paper envelopes only, no database will be utilized.

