## **5 Sample Size Determination**

A sample size of 40 total subjects, twenty to begin treatment with each of the two study arms, was selected as sufficient to perform a preliminary assessment of the differences between the two repetitive transcranial magnetic stimulation (rTMS) therapies for MDD. The sample size is not based on formal power requirements for a statistical hypothesis test but is based on a desire to obtain a reasonable initial data set for exploratory and planning purposes.

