### **6.2 Analysis Populations**

*The following analysis populations are defined for analysis:*

1. **Intent-to-treat (ITT):** *The ITT population is defined as all subjects randomized.*
2. **Modified Intent-to-Treat (mITT):** *The mITT population is defined as all subjects in the ITT population where treatment was initiated.*
3. **Per protocol (PP):** *The PP population is defined as all subjects in with no significant protocol deviation, or adverse event that could compromise the validity of their assessments.*
4. **Safety (SAF):** *The SAF population is defined as all subjects that were exposed to any study device or treatment.*

The primary analysis set for efficacy endpoints and results will be the mITT set, with any other analysis sets defined as optional and supportive. The primary analysis set for safety endpoints and results will be the SAF set, with any other analysis sets defined as optional and supportive.

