### **6.3 Handling of Missing Data**

All attempts will be made to limit the amount of missing data. Unless otherwise specified, no attempt will be made to impute missing data. If a data point is missing, that data point will not contribute to that portion of the analysis. The number of evaluable observations will be reported in analysis so that extent of missing data can be assessed.

In the case of partial adverse event onset date or date of death, the unknown portion of the date of the event will be imputed. If the month and year are known, the 15th of the month will be used for analysis. In the rare case that the date is fully unknown, the date will be imputed as the Date of first day of the Dose Ramp Phase. Imputation of partial dates is subject to the condition that it must occur on or after the informed consent date. In the case where the imputed date is prior to the informed consent date,

Statistical Analysis Plan		Page 10 of 18
Sponsor Neuronetics	Study Comfort Start	Version 1.0

the date of informed consent will be used. As death cannot occur before any documented subject contact, for date of death the imputed date of death must occur on or after last known contact in study.

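### Whole-trial comfort analysis (a) counts 40 X and 40 Y averages, but a patient who leaves before the first switch has only one, and the SAP has no rule for that patient

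*SAP*

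**What the plan says.** SAP 6.6.2 lists several comfort analyses, one of which is to become the primary analysis. Two of them pool X and Y scores. The first, lettered (a), covers the ramp and crossover phases. It averages the 3:45 and 18:45 scores each day, averages the days by protocol for each patient, and finishes by "comparing the average of the 40 X averages to the average of the 40 Y averages". The second ("Average of all the patient scores for all Crossover Phase treatments") uses Crossover Days only and gives the same counts of 40 and 40.

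Four other provisions decide who has which average:

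- **Planned number** (SAP 5): "A sample size of 40 total subjects, twenty to begin treatment with each of the two study arms".
- **Analysis set** (SAP 6.2): "The mITT population is defined as all subjects in the ITT population where treatment was initiated". Data on both protocols are not required.
- **Missing data** (SAP 6.3): nothing is imputed, and "If a data point is missing, that data point will not contribute to that portion of the analysis".
- **Replacement** (Protocol 13.2): "Subjects withdrawn from the study will not be replaced".

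Protocol 13.1 keeps a patient on the randomised protocol for one to five ramp sessions and makes the first switch at Crossover Visit 1. Protocol 10.1 lets patients stop at any time. For assessments that include crossovers, Protocol 18.2 commits to a method that handles period, repeated measures and order. SAP 6.6.2 makes the same method optional.

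**The concern.** Analysis (a) is meant to describe a difference between protocols in the same patients. A patient who leaves in the ramp has an average on the first protocol only. If that average goes into one mean with nothing opposite it, the difference between that patient and the rest becomes part of the estimated treatment difference.

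Leaving may well be related to the score. Discontinuation for discomfort is a secondary outcome (SAP 6.6.3), and Protocol 10.2 accepts that starting on standard Dash may bring some additional discomfort. If more high scorers leave on Dash, the error favours SoftStart, which is the direction of the one-sided test. The SAP does not say whether such a patient stays in one mean, is dropped from the contrast, or enters through a model.

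**Working it through.** **1. Reproduce the plan's count.** Let dY be the Dash-first and dX the SoftStart-first patients who leave before the switch, with everyone having at least one score.

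- X averages: nX = 40 − dY
- Y averages: nY = 40 − dX
- Patients with both: 40 − dX − dY

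With dX = dY = 0, the 20 + 20 patients give 40 X and 40 Y averages, as stated. Any loss in the ramp breaks the count.

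**2. Shift in analysis (a).** Suppose leavers score D points (0–100 scale) above the other patients on the same protocol. The unpaired difference, Y minus X, moves by

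D × (dY/nY − dX/nX).

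| dY | dX | nX | nY | Pairs | Shift at D = 10 / 20 / 30 |
|---|---|---|---|---|---|
| 0 | 0 | 40 | 40 | 40 | 0 / 0 / 0 |
| 2 | 0 | 38 | 40 | 38 | +0.5 / +1.0 / +1.5 |
| 4 | 0 | 36 | 40 | 36 | +1.0 / +2.0 / +3.0 |
| 4 | 2 | 36 | 38 | 34 | +0.50 / +0.99 / +1.49 |
| 4 | 4 | 36 | 36 | 32 | 0 / 0 / 0 |
| 0 | 4 | 40 | 36 | 36 | −1.0 / −2.0 / −3.0 |

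A positive shift favours SoftStart. The leaver counts and D are assumptions; the documents give neither.

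**3. Expected bias.** Simulation, 4,000 trials per row. Assumed: Dash mean 40, between-patient SD 20, SD of each protocol average 10/√2 ≈ 7, and leaving whenever the first-protocol average exceeds the cut-off.

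| True difference | Cut-off | Mean leavers, Y-first / X-first | Unpaired | Paired |
|---|---|---|---|---|
| 0 | 75 | 1.00 / 1.01 | −0.05 | −0.04 |
| 0 | 65 | 2.40 / 2.40 | 0.01 | 0.00 |
| 5 | 75 | 1.01 / 0.60 | 5.36 | 4.96 |
| 5 | 65 | 2.40 / 1.59 | 5.49 | 4.88 |
| 10 | 75 | 0.98 / 0.33 | 10.58 | 9.92 |
| 10 | 65 | 2.39 / 1.03 | 10.93 | 9.86 |

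With no true effect there is no bias. With a true effect the unpaired estimate is 6–10% too large (0.58/10 to 0.49/5). The paired estimate is up to about 2% too small (0.12/5), because those who stay are a selected group.

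**4. Noise.** A second simulation (1,500 trials per scenario) used one to five ramp sessions plus four alternating sessions, SD 20 between and 10 within patients, with leaving concentrated in sessions scoring above 65. With no true effect and about 2, 4 and 5 one-protocol leavers, the SD of the unpaired against the paired estimate was 1.79 v 1.38, 2.11 v 1.45 and 2.47 v 1.56, that is 30%, 46% and 58% larger. Hand check for 4 leavers: each adds about ±30/40 at random, a variance of 4 × 30²/40² = 2.25, and √(1.45² + 2.25) = 2.09, close to 2.11.

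**5. Crossover Phase analysis.** A patient who leaves before the switch has no Crossover Day, so adds nothing to either mean; only the count falls below 40. One-sided entry needs a patient who leaves after Crossover Visit 1 and before Crossover Visit 2. That patient has only the second protocol's average, so the sign reverses. Four Dash-first patients lost in that window, scoring 30 points higher, leave 40 X and 36 Y averages and shift the result by −4 × 30/40 = −3.0, against SoftStart.

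**The case against.** The strongest reply is that the SAP never says the comparison is unpaired. It forms both averages for each patient, does not call the t-test independent, and is to be read with a protocol that commits to a repeated-measures crossover method. Under such a method the one-sided entry largely disappears. This stands as far as it goes: the defect is a missing rule, not an instruction to compare unpaired. But the SAP makes that method optional, and its nonparametric example is the rank sum test. Nothing binding keeps a one-protocol patient out of a single mean.

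The size is also modest. In the second simulation, with a true benefit of 20% (about 8.0 points), the unpaired estimates were 8.24, 8.57 and 8.82. Those errors of 0.24 to 0.82 are below the estimate's own null SD of 1.79 to 2.47. The paired estimates of 7.81, 7.70 and 7.58 err by 0.19 to 0.42 the other way. Leaving because of high scores is an inference: intensity can be lowered for intolerance, patients below 120% MT still cross over, and some withdrawal reasons, such as pregnancy, have no evident link to comfort. The study is exploratory ("The sample size is not based on formal power requirements for a statistical hypothesis test"). All of this stands and limits the weight of the point.

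A reader might also infer that leavers vanish from the report. The documents do not support that. SAP 6.3 reports evaluable observations, SAP 6.4 reports early exits by reason, and SAP 6.6.3 includes discomfort discontinuations. What is missing is the number of one-protocol patients by starting arm.

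**Conclusion.** The point holds for whole-trial analysis (a). The 40 and 40 are right only with no loss before Crossover Visit 1, and comparing the two means as written lets a ramp leaver count on one side. The sure consequence is extra noise whenever leavers differ from stayers. A shift arises when leavers differ in number or score between starting arms: +3.0 points for 4 Dash-first leavers 30 points higher and no SoftStart-first leavers, zero if balanced, negative if reversed. These figures rest on assumed leaver counts, score gaps, SDs and cut-offs.

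Two stronger readings are not supported. The first is that ramp leavers distort both pooled analyses; in the Crossover Phase analysis they enter neither side. The second is that the plan would manufacture a SoftStart benefit; with no true effect and leaving driven only by score, "with a 1:1 allocation ratio" balances leavers in expectation and the expected bias is zero. Restricting to patients with both averages is not a complete answer either, since they are a selected group.

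**What to change.** In SAP 6.6.2, for both pooled analyses:

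1. Estimate the X–Y difference within patients, using all mITT sessions in a model with a patient effect that accounts for period and sequence. Change the SAP's *may* to the protocol's *will* for the crossover method.
2. Support it with the paired difference in patients who have both averages.
3. Replace 40 with the number of patients contributing to each average and to the within-patient contrast.
4. Tabulate one-protocol patients by starting arm and reason for leaving.

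A sensitivity analysis that sets a leaver's missing average equal to the observed one, so assuming no benefit, is optional.

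The cost is SAP wording and one extra table, with no change to study conduct. The downside is a reported n for the contrast that may fall below 40.
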